Appendix 3: Liver Chemistry Increased Monitoring Criteria

Table 10 summarizes requirements for follow-up of liver function test abnormalities.

 Table 10
 Liver Chemistry Increased Monitoring Criterion and Follow-Up

Criterion	Actions
Elevated ALT and/or AST: • Above 2 × Baseline, or	 Participant can continue study drug at the discretion of the Investigator
• Above 5 × ULN	 Repeat measurement of LFTs (including ALT, AST, ALP, and total bilirubin) will be performed within 48 hours to
Elevated ALP above 3 × ULN	confirm the abnormalities and to determine if they are increasing or decreasing. If total bilirubin is increased above the upper limit of normal, there should be a reflex to direct and indirect bilirubin.
	 PT/INR and albumin will be tested when significantly abnormal liver function is observed and repeated with repeat measurement of LFTs.
	 Upon confirmation of elevated LFTs, close observation by repeating LFTs every 24 to 72 hours will be initiated immediately.
	 Frequency of monitoring can be decreased as LFTs decrease at the Investigator's discretion.
	 The Investigator will collect detailed information on concomitant symptoms, new medications, drug or alcohol exposure, etc., to identify possible cause of abnormal LFTs.
	 Close observation on abnormal LFTs will last until the parameters return to baseline, or to a stable level judged by the Investigator.

Abbreviations: ALP = alkaline phosphatase; ALT = alanine transaminase; AST = aspartate transaminase; INR = international normalized ratio; LFT = liver function test; PT = prothrombin time; ULN = upper limit of normal

Note: If any of the following laboratory abnormalities is confirmed by repeat testing, considered related to the study drug and does not have alternative etiology, study drug may be discontinued at the discretion of the Investigator in accordance with Section 7.1.2, and the Medical Monitor should be informed (repeat test should be performed within 48-72 hours once initial abnormality is detected):

- $\circ \qquad \text{ALT or AST} > 8 \times \text{ULN}$
- $\circ~$ ALT or AST $>5\times$ ULN for more than 1 week during study drug administration
- ALT or AST > 2 × Baseline with the appearance of fatigue, nausea, vomiting, right upper quadrant pain or tenderness, fever, rash, and/or eosinophilia (> 5%)
- ALT or AST > 2 × Baseline and total bilirubin > 2 × ULN or INR > 1.5 for more than 1 week, confirmed with a repeat assessment
- \circ ALP > 5 x ULN
- \circ ALP > 3 x ULN and total bilirubin > 2x ULN

Appendix 4: Fridericia's Formula

A single 12-lead ECG will be obtained as outlined in the Schedule of Activities (see Section 1.1) using an ECG machine that automatically calculates the heart rate and measures PR, QRS, and QT intervals. QTc will be calculated using Fridericia's Formula as outlined below.

The Investigator will review the ECGs for any clinically significant abnormalities.

Fridericia's Formula:

QTc = QT/(RR^0.33) http://www.thecalculator.co/health/QTc-Calculator-385.html

Appendix 5: Chronic Kidney Disease Epidemiology Collaboration (CKD-EPI) Formula to Estimate Glomerular Filtration Rate

 $GFR = 141 \times \min(S_{cr}/\kappa, 1)^{\alpha} \times \max(S_{cr}/\kappa, 1)^{-1.209} \times 0.993^{Age} \times 1.018 \text{ [if female]} \times 1.159 \text{ [if black]}$

Abbreviations / Units:

SCr (standardized serum creatinine) = mg/dL $\kappa = 0.7$ (females) or 0.9 (males) $\alpha = -0.329$ (females) or -0.411 (males) min = indicates the minimum of SCr/ κ or 1 max = indicates the maximum of SCr/ κ or 1 age = years

Appendix 6: Adverse Events: Definitions and Procedures for Recording, Evaluating, Follow-up, and Reporting

AE Definition

- An AE is any untoward medical occurrence in a patient or clinical study patient, temporally associated with the use of study drug, whether or not considered related to the study drug.
- NOTE: An AE can therefore be any unfavorable and unintended sign (including an abnormal laboratory finding), symptom, or disease (new or exacerbated) temporally associated with the use of study drug.

Events Meeting the AE Definition

- Any safety assessment (eg, ECG, radiological scans, vital signs measurements), including those that worsen from baseline, considered clinically significant in the medical and scientific judgment of the Investigator (ie, not related to progression of underlying disease).
- A clinical condition or symptom associated with an abnormal laboratory test result (e.g. hematology, clinical chemistry, or urinalysis). An abnormal laboratory test that is not accompanied with other signs or symptoms should not be reported as an AE.
- Exacerbation of a chronic or intermittent pre-existing condition including either an increase in frequency and/or intensity of the condition.
- New conditions detected or diagnosed after study drug administration even though it may have been
 present before the start of the study.
- Signs, symptoms, or the clinical sequelae of a suspected drug-drug interaction.
- Signs, symptoms, or the clinical sequelae of a suspected overdose of either study drug or a concomitant medication. Overdose per se will not be reported as an AE/SAE unless it is an intentional overdose taken with possible suicidal/self-harming intent. Such overdoses should be reported regardless of sequelae.

Events **NOT** Meeting the AE Definition

- Abnormal laboratory findings or other abnormal safety assessments that are associated with an
 underlying disease present at baseline without worsening, unless judged by the Investigator to be more
 severe than expected for the patient's condition.
- An abnormal laboratory test that is not accompanied with other signs or symptoms.
- The disease/disorder being studied or signs, or symptoms of the disease/disorder being studied, unless more severe than expected for the patient's condition.
- Medical or surgical procedure (eg, endoscopy, appendectomy): the condition that leads to the procedure is the AE.
- Situations in which an untoward medical occurrence did not occur (social and/or convenience admission to a hospital).
- Anticipated day-to-day fluctuations of pre-existing disease(s) or condition(s) present or detected at the start of the study that do not worsen.

Definition of SAE

An SAE is an AE that meets the following criteria:

An SAE is defined as any untoward medical occurrence that, at any dose:

a. Results in death

b. Is life-threatening

The term 'life-threatening' in the definition of 'serious' refers to an event in which the patient was at risk of death at the time of the event. It does not refer to an event, which hypothetically might have caused death, if it were more severe.

c. Requires inpatient hospitalization or prolongation of existing hospitalization

- In general, hospitalization signifies that the patient has been detained (usually involving at least an overnight stay) at the hospital or emergency ward for observation and/or treatment that would not have been appropriate in the physician's office or outpatient setting. Complications that occur during hospitalization are AEs. If a complication prolongs hospitalization or fulfills any other serious criteria, the event is serious. When in doubt as to whether "hospitalization" occurred or was necessary, the AE should be considered serious.
- Hospitalization for elective treatment of a pre-existing condition that did not worsen from baseline is not considered an AE.

d. Results in persistent disability/incapacity

- The term disability means a substantial disruption of a person's ability to conduct normal life functions.
- This definition is not intended to include experiences of relatively minor medical significance such as uncomplicated headache, nausea, vomiting, diarrhea, influenza, and accidental trauma (eg, sprained ankle) which may interfere with or prevent everyday life functions but do not constitute a substantial disruption.

e. Is a congenital anomaly/birth defect

f. Other situations:

- Medical or scientific judgment should be exercised in deciding whether SAE reporting is appropriate in
 other situations such as important medical events that may not be immediately life-threatening or result
 in death or hospitalization but may jeopardize the patient or may require medical or surgical intervention
 to prevent one of the other outcomes listed in the above definition. These events should usually be
 considered serious.
- Examples of such events include invasive or malignant cancers, intensive treatment in an emergency room or at home for allergic bronchospasm, blood dyscrasias or convulsions that do not result in hospitalization, or development of drug dependency or drug abuse.

If an event does not meet the AE definition, then it cannot be an SAE even if serious conditions are met (eg, hospitalization for signs/symptoms of the disease under study, death due to progression of disease).

Recording and Follow-Up of an AE and/or SAE

AE and SAE Recording

- When an AE and/or SAE occurs, it is the responsibility of the Investigator to review all documentation (eg, hospital progress notes, laboratory reports, and diagnostics reports) related to the event.
- The Investigator will then record all relevant AE and/or SAE information in the eCRF.
- It is **not** acceptable for the Investigator to send photocopies of the patient's medical records to the Sponsor or designee in lieu of completion of the AE or SAE eCRF.
- There may be instances when copies of medical records for certain cases are requested by the Sponsor or designee. In this case, all patient identifiers, with the exception of the patient number, will be redacted on the copies of the medical records before submission to the Sponsor or designee.
- The Investigator will attempt to establish a diagnosis of the event based on signs, symptoms, and/or other clinical information. Whenever possible, the diagnosis (not the individual signs/symptoms) will be documented as the AE and/or SAE.

Assessment of Intensity

The Investigator will be asked to provide an assessment of the severity of the AE using NCI CTCAE v5.0 categories as follows:

- Grade 1: Mild; asymptomatic or mild symptoms; clinical or diagnostic observations only; intervention not indicated.
- Grade 2: Moderate; minimal, local, or noninvasive intervention indicated; limiting age appropriate instrumental ADL.
- Grade 3: Severe or medically significant but not immediately life-threatening; hospitalization or prolongation of hospitalization indicated; disabling; limiting self-care ADL.
- Grade 4: Life-threatening consequences; urgent intervention indicated.
- Grade 5: Death related to AE.

For detailed organ system AE severity grading, please refer to NCI CTCAE v5.0: https://ctep.cancer.gov/protocoldevelopment/electronic applications/docs/CTCAE v5 Quick Reference 8.5x11.pdf

Assessment of Causality

- The Investigator is obligated to assess the relationship between study drug and each occurrence of each AE and/or SAE.
- The Investigator (or designee) will make a determination of the relationship of the AE to the study drug using a 4-category system according to the following guidelines:
 - Not Related: The AE is definitely caused by the subject's clinical state or the study procedure/conditions.
 - **Unlikely Related:** The temporal association between the AE and the drug is such that the drug is not likely to have any reasonable association with the AE.
 - Possibly Related: The AE follows a reasonable temporal sequence from the time of drug administration but could have been produced by the subject's clinical state or the study procedures/conditions.
 - Related: The AE follows a reasonable temporal sequence from administration of the drug, abates upon discontinuation of the drug, follows a known or hypothesized cause effect relationship, and (if appropriate) reappears when the drug is reintroduced.
- For each AE and/or SAE, the Investigator **must** document in the medical notes that he/she has reviewed the AE and/or SAE and has provided an assessment of causality.
- There may be situations in which an SAE has occurred and the Investigator has minimal information to
 include in the initial report to the Sponsor or designee. However, it is very important that the Investigator
 always make an assessment of causality for every event before the initial transmission of the SAE data to
 the Sponsor or designee.
- The Investigator may change his/her opinion of causality in light of follow-up information and send a SAE follow-up report with the updated causality assessment.

• The causality assessment is one of the criteria used when determining regulatory reporting requirements.

Follow-up of AEs and SAEs

- The Investigator is obligated to perform or arrange for the conduct of supplemental measurements and/or evaluations as medically indicated or as requested by the Sponsor or designee to elucidate the nature and/or causality of the AE or SAE as fully as possible. This may include additional laboratory tests or investigations, histopathological examinations, or consultation with other health care professionals.
- If a patient dies during participation in the study or during a recognized follow-up period, the Investigator will provide the Sponsor or designee with a copy of any post-mortem findings including histopathology.
- New or updated information will be recorded in the originally completed CRF.
- The Investigator will submit any updated SAE data to the Sponsor or designee within 24 hours of receipt of the information.

Reporting of SAEs

SAE Reporting to Sponsor or designee via Paper CRF

- Email transmission of the SAE paper Report Form is the preferred method to transmit this information to the Labcorp Drug Development Patient Safety Group ([contact]).
- Notification by facsimile transmission to the Labcorp Drug Development Patient Safety Group is also acceptable ([name])
- Initial notification via telephone or email does not replace the need for the Investigator to complete, sign, and return the SAE report form within the designated reporting time frames.
- Contacts and additional instructions for SAE reporting can be found in in the Study Procedures Manual provided.

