8.1.9. Clinical Laboratory Assessments

See Appendix 1 for the list of clinical laboratory tests to be performed and refer to the Schedule of Activities (Section 1.3) for the timing and frequency.

The Investigator must review the laboratory report, document this review, and record any AEs per the guidance in Appendix 6. The laboratory reports must be filed with the source documents.

Shifts of clinically significant Grade 3 or Grade 4 laboratory abnormalities or any clinically significant laboratory abnormalities considered possibly related to study drug in the opinion of the Investigator should be repeated within 48-72 hours and followed to resolution or until stable.

All protocol-required laboratory assessments, as defined in Appendix 1, must be conducted in accordance with the laboratory manual and the Schedule of Activities.

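### Appendix 6 bars symptom-free laboratory abnormalities from AE reporting even when they lead to study drug being stopped or are serious, so such a patient can have no AE record

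*Protocol*

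**What the plan says.** In Protocol Appendix 6, the NOTE under the AE definition names laboratory findings as possible AEs: "An AE can therefore be any unfavorable and unintended sign (including an abnormal laboratory finding), symptom, or disease (new or exacerbated".

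The list of events that meet the definition opens with a clinical-significance route: "Any safety assessment (eg, ECG, radiological scans, vital signs measurements), including those that worsen from baseline, considered clinically significant". The next bullet deals with laboratory tests and ends: "An abnormal laboratory test that is not accompanied with other signs or symptoms should not be reported as an AE". The list of events that do not meet the definition repeats the bar without qualification: "An abnormal laboratory test that is not accompanied with other signs or symptoms". On seriousness, the same appendix adds: "If an event does not meet the AE definition, then it cannot be an SAE even if serious conditions are met".

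Section 8.1.9 sends laboratory review back to this appendix: "The Investigator must review the laboratory report, document this review, and record any AEs per the guidance in Appendix 6".

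Section 7.1.2 meanwhile lets the Investigator stop study drug on liver laboratory criteria, and requires a stop for certain TSH results. In both cases a repeat test must confirm the value.

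In the SAP, Section 8.2 builds TEAEs from AE records, and Section 8.2.2 draws the table of TEAEs that led to stopping drug as a subset of those records. Section 6.1 tabulates early treatment discontinuation with reasons. Section 8.3.1 and its Table 11 tabulate laboratory abnormalities separately from AEs.

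**The concern.** Patient incidence of TEAEs is a secondary endpoint, and discontinuation because of an AE is a standard measure of tolerability. Both depend on an AE record existing. The bar on symptom-free laboratory tests is stated twice, without an exception for the cases where a record matters most: the drug was stopped, treatment was given, or a seriousness criterion was met.

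Two things are at stake. First, the AE tables and the disposition table can disagree about the same patient. Second, an event that is not an AE falls outside SAE reporting, including the 24-hour report to the Sponsor in Section 8.5.1. Both drug classes have been associated with liver enzyme increases (Section 2.3), so a laboratory-only liver event is a foreseeable presentation here.

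**Working it through.** The protocol and SAP give no figure to reproduce. The check is whether any text restores AE reporting, and what happens to a patient if none does.

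**Step 1. Is there an exception to the bar?** The candidates are:

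- *The NOTE.* It says a laboratory finding can be an AE. It is general, and the two bullets that follow are specific.
- *The clinical-significance bullet.* Its examples are ECGs, scans and vital signs. The list is not exhaustive, and the first exclusion bullet speaks of "Abnormal laboratory findings or other abnormal safety assessments", which suggests that laboratory tests are one kind of safety assessment. A site could read them in, but the very next bullet says the opposite for symptom-free tests.
- *The more-severe-than-expected clause.* It applies only to findings tied to a disease already present at baseline. It is not attached to the symptom-free bar.
- *Section 8.1.9.* It refers back to Appendix 6 and so supplies no override.
- *Section 7.1.2.* It does not say that a stop on laboratory criteria must be recorded as an AE.

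No explicit exception was found. The appendix's own severity scale also sits badly with the bar, since Grade 1 includes asymptomatic events known only from diagnostic observation.

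**Step 2. Can drug be stopped on laboratory values alone?** The liver list in Section 7.1.2 has six criteria:

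| Criterion | What it needs |
|---|---|
| ALT or AST > 8 × ULN | one analyte, no symptom |
| ALT or AST > 5 × ULN for more than 1 week | one analyte, no symptom |
| ALT or AST > 2 × Baseline plus clinical features | symptom, sign or eosinophilia |
| ALT or AST > 2 × Baseline plus bilirubin > 2 × ULN or INR > 1.5 | a second laboratory test |
| ALP > 5 × ULN | one analyte, no symptom |
| ALP > 3 × ULN plus bilirubin > 2 × ULN | a second laboratory test |

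So 3 of 6 can be met by one analyte with no symptom. All six also require the abnormality to be confirmed by a repeat test, judged drug-related and without another cause.

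**Step 3. Follow one patient.** Assume a confirmed, related ALT above 8 × ULN, or ALP above 5 × ULN, no symptoms, drug stopped, and no diagnosis recorded.

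- AE record: none, under the two bullets.
- TEAE incidence (SAP 8.2, 8.2.2): this event is absent. The patient counts only if some other TEAE occurred.
- TEAEs leading to drug discontinuation (SAP 8.2.2): absent.
- SAE: not possible, even if a seriousness criterion were met.
- Disposition (SAP 6.1): counted as an early treatment discontinuation, with a reason.
- Laboratory tables (SAP 8.3.1, Table 11): counted. ALT above 8 × ULN falls in the 5 to < 10 × ULN band or higher; ALP above 5 × ULN falls in the ≥ 2 × ULN row.

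**Step 4. Size per patient.** With the planned 20 patients in an arm, one such patient changes that arm's AE-discontinuation figure by 1/20 = 5 percentage points.

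**Step 5. How many patients?** The documents give no expected number. Section 2.3 reports no TERN-501 subject with ALT ≥ 2 × ULN in the single- and multiple-dose cohorts (healthy subjects, up to 14 days of dosing). Section 2.2.2.2 reports no TERN-101 patient with a treatment-emergent ALT > 2 × ULN over 12 weeks. The number may be few or none. Section 2.3 also says that neither TERN-501 alone nor the combination has been evaluated in a NASH population.

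**The case against.** The strongest reply is that the bullets are a deliberate narrowing. The NOTE says only what an AE can be; the bullets then keep incidental laboratory values out of the AE tables, which is a legitimate aim. That explains why the bar exists. It does not explain why it has no exception for a value that ends treatment or is serious.

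A second reply is that a diagnosis can be recorded. Appendix 6 admits newly detected or diagnosed conditions, asks for a diagnosis where possible, and lists blood dyscrasias among its SAE examples. A confirmed, related ALT above 8 × ULN with no other cause could well be entered as a liver diagnosis. A second abnormal test, such as AST raised alongside ALT, might also be taken as another sign. These routes are real and narrow the gap. They depend on how each site reads the text, so they do not close it. Further SAE instructions sit in a Study Procedures Manual that is not among the documents.

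A third reply is that nothing is lost from the data, and this largely stands. Section 7.1.1 provides blinded review of laboratory values. Section 8.1.9 requires repeat testing within 48 to 72 hours and follow-up for "Shifts of clinically significant Grade 3 or Grade 4 laboratory abnormalities or any clinically significant laboratory abnormalities considered possibly related to study drug". Appendix 3 sets closer liver monitoring, and Protocol 9.4.5 and SAP 8.3.1 tabulate graded abnormalities. TEAE incidence is descriptive and the reporting rule is the same in every blinded arm. What is missing is the AE record and whatever depends on it.

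Three stronger readings are tempting and not supported:

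- *One laboratory value can take a patient off drug unrecorded.* The liver and TSH criteria require confirmation by repeat testing, and one of them requires more than a week of elevation.
- *Four of seven laboratory triggers leave no AE record.* Adding the TSH trigger to Step 2 gives (3 + 1) of (6 + 1), but this counts rules, not patients, and is an upper bound. The TSH stop needs a clinically significant value or a need for new therapy, so a thyroid diagnosis may well be recorded.
- *Section 7.1.2 should be rewritten too.* Sending all laboratory-only liver events to its liver list would replace a mandatory stop for related Grade 3 or above AEs with a discretionary one, and that list has no criterion for isolated GGT or bilirubin. Requiring a repeat test before other mandatory Grade 3 stops would add a precondition that the current rule does not have.

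**Conclusion.** The concern holds in a limited form. Appendix 6 is inconsistent on symptom-free laboratory abnormalities, and its specific bullets carry no exception for action taken or seriousness. Followed as written, they leave a patient stopped on confirmed laboratory values alone without an AE record, so the AE tables and the disposition table disagree and the event cannot be reported as an SAE.

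This rests on three assumptions: the site follows the bullets rather than the NOTE, it does not treat a second abnormal test as a sign, and no diagnosis is recorded. The effect is on classification and reporting, not on whether the abnormality is seen. The size is 5 percentage points of an arm's AE-discontinuation figure per affected patient (assuming 20 treated), with an unknown number of patients that may be zero. The wording is worth correcting because it touches a secondary endpoint and can block SAE reporting.

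**What to change.** Add the same words to both Appendix 6 bullets: *unless it leads to treatment or to study drug interruption or discontinuation, or meets a seriousness criterion*. A further exception for clinical significance, matching the one for other safety assessments, is optional. Make no change to Section 7.1.2. Tell sites of the clarification.

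This is a cheap improvement, and incidental symptom-free values stay out of the AE tables. It costs a few more AE and SAE records and a slightly higher TEAE rate. It also has a knock-on effect that should be accepted knowingly. A newly recorded, related laboratory AE of Grade 3 or above would fall under the existing mandatory stop in Section 7.1.2. It would also count toward the study-stopping criteria in Section 7.1.1, which are met by three patients with the same related Grade III event, two with the same related Grade IV event, or one with a related Grade V event.
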